#### **Preparation of the everolimus dispersal:**

The patient will receive everolimus tablets for oral suspension as a suspension only. The everolimus tablets for oral suspension will be administered orally once daily at the same time every day. It will be given either consistently with food or consistently without food. The suspension will be administered immediately after preparation. The suspension will be discarded if not administered within 60 minutes after preparation.

Prepare suspension in water only.

#### **Using an oral syringe:**

- Place the prescribed dose of everolimus tablets for oral suspension into a 10-mL syringe. Do not exceed a total of 10 mg per syringe.

If higher doses are required, prepare an additional syringe. Do not break or crush tablets.

- Draw approximately 5 mL of water and 4 mL of air into the syringe.
- Place the filled syringe into a container (tip up) for 3 minutes, until the everolimus tablets for oral suspension are in suspension.
- Gently invert the syringe 5 times immediately prior to administration.
- After administration of the prepared suspension, draw approximately 5 mL of water and 4 mL of air into the same syringe, and swirl the contents to suspend remaining particles. Administer the entire contents of the syringe.

#### **Using a small drinking glass:**

- Place the prescribed dose of everolimus tablets for oral suspension into a small drinking glass (maximum size 100 mL) containing approximately 25 mL of water. Do not exceed a total of 10 mg of everolimus tablets for oral suspension per glass. If higher doses are required, prepare an additional glass. Do not break or crush tablets.

- Allow 3 minutes for suspension to occur.
- Stir the contents gently with a spoon, immediately prior to drinking.

CONFIDENTIAL

This document and information is the property of the NYU School of Medicine and Langone Medical Center. Do not disclose or use except as authorized in writing by the study IND sponsor

- After administration of the prepared suspension, add 25 mL of water

Everolimus tablets for oral suspension should NOT be taken with grapefruit or Seville orange juice or with other effectors of CYP3A4 (other than known AEDs or other medications identified at Visit 1 as one of their baseline medications).

**NOTE:** Everolimus should be opened only at the time of administration as drug is both hygroscopic and light-sensitive.

### **5.2 Treatment Regimen**

Everolimus will be self-administered (by the patient or parent at home during the 7-21 days prior to neurosurgery). The investigator will instruct the patient to take the study drug exactly as specified in the protocol.

Patients who are eligible for the active treatment group with TSC or FCD only will receive everolimus. After a minimum of three patients are treated for 7 days (Table 2), if there is no evidence of serious adverse effects or other dose-level tolerability and safety issues, we will extend the treatment duration by a maximum of one week. Again, after a minimum of three patients are treated for two weeks without evidence of serious adverse effects or other dose-level tolerability and safety issues, we will extend the treatment duration to three weeks. For patients treated longer than two weeks, an everolimus blood level will be obtained after 10-12 days and used to adjust dose to maintain a serum level of 5-10 ug/ml. to revisit escalation and numbers. If one patient at a dose duration has a serious adverse effect during a treatment cohort period (e.g., 7 days), then up to 6 patients are treated with that dose duration. If there are 2 or more serious adverse events among the 6 patients, then the duration is dropped back to the prior level. If there are no events in 3 patients or 1 event in 6 patients, then the dose duration is escalated to the next level. At the 3 week dose duration, 6 patients will be treated even if there are no events among the first 3 patients.

Table 2: Dosing Escalation for Serial Cohorts

Serial Cohort Number	Minimum # of patients if no Grade 3 or 4 adverse event or serious adverse events	Minimum # of patients if one Grade 3 or 4 adverse event or serious adverse events ^	Duration of everolimus therapy	Result of one serious adverse events including wound healing problem and serious infection	Result of two serious adverse events including wound healing problem and serious infection
1	3	9	7 days		
2	3	6	14 days	Add additional patients to Cohort 1	Return to cohort one, no potential for longer treatment duration
3	1-3	6	21 days	Add additional patients to Cohort 2	Return to cohort two, no potential for longer treatment duration

^ Adverse events as defined by CTAE v.4.0

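### The Section 5.2 prose and Table 2 give conflicting duration-escalation rules, the prose does not fit nine treated patients, and the post-operative follow-up required before escalation is not named

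*Combined protocol and SAP*

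**What the plan says.** The Study Summary plans 9 treated patients and 12 controls. Section 5.2 then governs how treated patients move between durations.

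- **Prose, opening condition.** At least three patients are treated at a duration, with "no evidence of serious adverse effects or other dose-level tolerability and safety issues", before it is lengthened.
- **Prose, expansion.** The rule begins "If one patient at a dose duration has a serious adverse effect during a treatment cohort period (e.g., 7 days" and continues "then up to 6 patients are treated with that dose duration".
- **Prose, escalation.** "If there are no events in 3 patients or 1 event in 6 patients, then the dose duration is escalated to the next level". Two or more SAEs among the 6 drop the duration back.
- **Prose, last step.** "At the 3 week dose duration, 6 patients will be treated even if there are no events among the first 3 patients".
- **Table 2, sizes.** One column is headed "Minimum # of patients if one Grade 3 or 4 adverse event or serious adverse events". As printed it reads 9, 6 and 6 for the three cohorts. The event-free column reads 3, 3 and 1-3.
- **Table 2, actions.** Under "Result of one serious adverse events including wound healing problem and serious infection", one SAE in the 14-day cohort adds patients to the 7-day cohort, and one in the 21-day cohort adds patients to the 14-day cohort. Two SAEs return treatment to the shorter duration with nothing longer afterwards.

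A drafting note, "to revisit escalation and numbers", still stands in the middle of the prose rule.

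On timing, Section 3.1 extends treatment once safety is judged assured for the cohort. Section 6.5 has the investigators review safety after each three-patient cohort completes the trial. Neither says what follow-up counts as completion.

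**The concern.** Safety is the plan's stated primary analysis, and lengthening exposure is the main decision made within the treated group. If two texts in one section direct different actions on the same data, the exposure of the next patient depends on which text the staff follow.

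The missing follow-up point matters because Visit 3 places the last dose on the morning of surgery. Surgical wound problems and wound infection, the harms of most concern, can therefore appear only after dosing ends. A cohort could be judged clear before they have had time to show.

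**Working it through.** **Inputs.** 9 treated patients and 18 months of recruitment (Study Summary); cohort sizes and actions (Section 5.2); infection rate 1.6% to 8.6%, mean 5.3% (sample size text in Section 7.3); half-life 30 hours (Section 1.5).

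**1. Planned total.** Table 2, no events: 3+3+1 = 7 up to 3+3+3 = 9, which accommodates 9. Prose, no events: 3+3+6 = 12, which is 3 more than planned.

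**2. The same data under each text, with 9 patients available.**

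| Data | Prose | Table 2 |
|---|---|---|
| One SAE at 7 days | Up to 6 at 7 days; 1 in 6 escalates; 9-6 = 3 left for 14 days | Minimum 9 at 7 days; 9-9 = 0 left |
| One SAE at 14 days | 3+6 = 9; extra patients receive 14 days | Extra patients receive 7 days; with the size column also applied, at least 3+1+6 = 10 |
| One SAE at 21 days | 6 at 21 days | Extra patients receive 14 days |
| One non-serious Grade 3 AE at 7 days | Cannot be determined | Minimum 9 at 7 days |

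In the first row no number is both at most 6 and at least 9. In the second and third rows the extra patients receive different durations. In the fourth, Table 2's size column counts the event. The prose expansion sentence does not, because Section 6.2.2 says a Grade 3 or 4 event is not automatically serious. The prose's wider opening condition might catch it, but that condition is undefined and carries no cohort size.

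**3. How likely the first row is.** The chance of exactly one infection in the first 3 patients is 3p(1-p)².

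- p = 1.6%: 3 × 0.016 × 0.984² = 4.6%
- p = 5.3%: 3 × 0.053 × 0.947² = 14.3%
- p = 8.6%: 3 × 0.086 × 0.914² = 21.6%

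These use the plan's background infection rates and assume that each infection counts as an SAE. They leave out wound-healing problems, other Grade 3/4 events and any drug effect.

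**4. Follow-up that could count as completion.**

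- Visit 6: 3 to 10 days after discharge.
- Section 6.2.1: the longer of 30 days or five half-lives after the last dose. Five half-lives are 5 × 30/24 = 6.25 days, so 30 days governs.
- Section 6.5: weekly wound inspection to six weeks (42 days) after surgery.

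Because the last dose is on the day of surgery, the second point closes 42-30 = 12 days before the third.

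**The case against.** Several points on the other side stand.

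- **Table 2 gives minimums.** A reader might infer that the two texts disagree on every cohort size. They do not. Both can be met with 6 at 14 days after one event, and 6 event-free patients at 21 days satisfies a minimum of 1-3. That 6 conflicts with the total of 9, not with Table 2.
- **Grade 3/4 events appear only in Table 2's size columns.** Both of its result columns use serious events, as the prose does. The event conflict is therefore confined to what enlarges a cohort.
- **The window.** A reader might infer that the prose leaves out post-operative wound events, because its expansion sentence refers to the treatment period. The documents do not support that. The phrase may simply name the cohort, the other prose conditions have no window, and Section 6.5 treats any wound breakdown, dehiscence or infection as an SAE.
- **Escalation is not ungated.** Section 3.1 makes it wait on a safety judgement, and Section 6.5 sends data to the safety board after every 3 completers. Only the end point is missing. The roughly 10 weeks in study in Section 3.1 does not supply it. With Visit 1 up to 6 weeks before Visit 2 and 1 to 3 weeks of dosing, it leaves anything from 10-6-3 = 1 to 10-0-1 = 9 weeks after surgery.
- **Other safeguards exist.** The study stops at two wound-healing or three serious-infection cases among 9 (Sections 7.3 and 7.1), and Section 4.4.1 withdraws a patient with a Grade 3 or 4 event. These limit harm, but they do not decide whether 14 or 21 days opens.

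**Conclusion.** The concern holds, and it should be fixed. The prose and Table 2 conflict on three matters: the 7-day cohort size after one event (at most 6 against at least 9, the whole treated group), where extra patients go after one SAE at 14 or 21 days, and which events enlarge a cohort. The prose also needs 12 event-free patients against 9 planned. Separately, the follow-up that must close before escalation is not named.

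The 7-day size conflict relies on the 9 printed in Table 2. The conflicts on action and on events, and the total of 12, do not depend on that cell.

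It is tempting to say that the larger sizes survive from a bigger design, since Section 4.4.1 still counts 18 treated patients. That is plausible, but it is an inference: the documents do not say how either set of sizes was derived.

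**What to change.** State one rule, identically in the Section 5.2 prose and Table 2, that fits 9 treated patients.

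1. **Sizes.** 3 at 7 days, 3 at 14 days, 1-3 at 21 days. Delete the sentence requiring 6 at 21 days, and the drafting note.
2. **One patient with a Grade 3/4 AE or an SAE at 7 or 14 days.** Expand that duration to 6, within the total of 9. Escalate on no more than 1 affected patient in 6, and only if places remain; otherwise longer durations do not open. After one SAE at 21 days, give the remaining places to 14 days, which is Table 2's existing action.
3. **Two patients with SAEs**, including wound-healing problems or serious infection. Return to the shorter duration with nothing longer later; at 7 days, 14 days does not open. Keep this action on SAEs, as both texts now do.
4. **Window and gate.** Count events from first dose through the six-week wound check. Define completion of the trial in Section 6.5 as that point, and open the next duration only after the Section 6.5 review of those data.

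**Cost.** The edits are wording in Section 5.2, Table 2 and Section 6.5. The wait is up to about six weeks at each of two steps. If accrual is even (an assumption), 18 × 30.44/9 = 60.9 days separate treated patients, so most of the wait falls in existing gaps. Controls can enrol meanwhile, as can patients at the current duration, though each of the latter uses one of the 9 places. Any expansion may mean that 21 days does not open. Grade 3/4 events caused by the surgery itself may also expand a cohort without a drug effect.

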### **1.5 Dose Rationale and Risk/Benefits**

The starting dose of everolimus for treatment patients will be 4.5 mg/m^2 once daily; adjust to attain trough concentrations of 5-15ng/ml. The dose will be adjusted for co-medications as outlined in section 5.1. However, these are initial doses often need to be titrated up to therapeutic everolimus serum levels (5 – 15 ng/mL). Since our everolimus treatment duration is 7-21 days and the half-life is 30 hours, the time to equilibration will be approximately 150 hours (6.25 days) and will not allow the investigators to adjust dose to achieve therapeutic levels in the initial groups of patients who will be treated for one to two weeks. We will double the dose in our study for patients who are taking an enzyme-inducing antiepileptic drug (EIAED) since serum everolimus levels will be lower due to increased hepatic metabolism.

After a minimum of three patients are treated for one week, if there is no evidence of serious adverse effects and other dose-level tolerability and safety issues, we will extend the treatment duration by a maximum of one week. Again, after a minimum of three patients treated for two weeks without evidence of serious adverse effects and other dose-level tolerability and safety issues, we will extend the treatment duration to three weeks. For patients treated longer than two weeks, an everolimus blood level will be obtained after 10-12 days and used to adjust dose to maintain a serum level of 5-10 ug/ml.

The most common adverse reactions (>30%) to everolimus treatment in TSC patients include stomatitis in patients with angiomyolipomas and stomatitis and respiratory tract infections in patients with SEGAs. Potential risks associated with 7-28 days of everolimus treatment include problems with wound healing and infections. Published data in patients with glioblastoma multiforme who underwent brain surgery, in a similar protocol to our study found no evidence of problems with wound healing or infection. There appears to increase the risk of infection and problems with wound healing in some patients who have received everolimus treatment and undergone organ transplantation but the risk of serious infection over control rates is not documented in patients with brain tumors or TSC.

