## **3 Study Design**

### **3.1 General Design**

This is a multi center open-label pilot clinical trial of patients with TRE, ages 2 to 50 years old, with TSC or FCD who are scheduled for epilepsy surgery. Patients will be treated with everolimus for 7 to 21 days prior to epilepsy surgery with extension of time from 7 to 21 days in successive cohorts of patients. The initial cohort of at least three patients will be treated for 7 days and after the safety of therapy is assured for this group, there will be an extension of the treatment to 14 days for at least three patients. This will be extended at one week intervals/three patient groups to a maximum treatment duration of 21 days. Resected brain tissue will be analyzed for activation of mTORC1 and mTORC2 signaling pathways, glutamatergic and GABA-ergic neurotransmission using histochemistry, genetic analysis, as well as extracellular field recordings in acute ex-vivo brain slices from surgery. A blood sample, collected at the time of surgery, will be analyzed for everolimus levels and VEGF-D. All patients will undergo standardized intra-operative ECoG recordings over the primary epileptogenic region and reviewed blindly.

Subjects will be in the study for approximately 10 weeks. We will study variables listed in specific aims 1 and 2 in TSC and FCD patients treated with 7 to 21 days of everolimus and compare these to untreated control patients with TRE and TSC or FCD. A concurrent comparison group of 12 subjects will also be enrolled. They will all be undergoing routine surgery for the diagnosis of TRE with TSC or FCD.

All study procedures will be performed at either the Comprehensive Epilepsy Center (CEC) with the exception of the surgery, which will be performed at Tisch Hospital

CONFIDENTIAL

This document and information is the property of the NYU School of Medicine and Langone Medical Center. Do not disclose or use except as authorized in writing by the study IND sponsor

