## **6 Study Procedures**

### **5.7 Visit 1 (Active/Control Patients)**

**NOTE:** This visit will occur within 6 weeks of Visit 2, which will be when patient will be entered into the study.

CONFIDENTIAL

This document and information is the property of the NYU School of Medicine and Langone Medical Center. Do not disclose or use except as authorized in writing by the study IND sponsor

After Informed Consent is obtained and study consent form is signed, Study Visit 1 will include the following, from interaction with the subject, and/or as applicable the subject's parents or guardian:

- A detailed review of the research subject's medical records and interview to ensure that the subject meets inclusion criteria and does NOT meet any of the exclusionary criteria.
- History of current seizure types and frequencies, concomitant medical or psychiatric disorders, and all prescribed and over-the-counter medications taken.
- Complete review of systems.
- Subject physical examination, including recording of vital signs, including height and weight to compute body mass index (BMI; see above) and body surface area (BSA), and neurological examination.
- Subject will be instructed to begin a daily seizure diary today that will be maintained and collected at the next visit.

**5.8 Visit 2 – (Active patients- 'NOTE: This visit will occur 7-21 days before surgery; patients/caretakers will be given Everolimus. )**

The following activities will be conducted and research subject information will be collected by interaction with the subject, and/or as applicable the subject's parents or guardian:

- Recent history will be reviewed for any change in their medical status or change in intake of prescribed or over-the-counter medication.
- Vital signs, physical and neurological examination.
- Collect and review seizure diary kept since Visit 1 and give new diary to be recorded until date of surgery. The protocol for study medication administration will be reviewed with the subject, and/or parent/guardian as applicable.
- Explanation of potential adverse events will be reviewed, as will the reporting of adverse events.
- Blood work: CBC and C-reactive protein (CRP). If not done prior to visit as part of PST (pre surgical testing)
- Review of the specific protocol for medication administration. (Active Patients Only at NYU CEC)

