#### Study drug dosing: (ACTIVE PATIENTS ONLY)

- On the day of surgery, the patient will take their last dose of everolimus with a 30 cc or less of water shortly after awakening and at least 3 hours before surgery
- A detailed seizure history during the prior week. A blood sample will be used for investigation per the IRB-approved protocol. This will include everolimus serum levels, systemic cytokines and mTOR activity levels. These samples will be batched and stored in -80 freezer until requested for analysis. )

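### Section 5.2 triggers cohort expansion on events in a window that, read literally, closes before surgery, and no text makes the existing cohort safety review a condition of lengthening treatment

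*Combined protocol and SAP*

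**What the plan says.** **Which events count.** The trigger for expanding a cohort in 5.2 is worded "If one patient at a dose duration has a serious adverse effect during a treatment cohort period (e.g., 7 days"). The sentences that follow (drop back on two or more serious events among six; escalate on no events in three or one in six) name no window. Table 2, in the same section, has a column headed "Result of one serious adverse events including wound healing problem and serious infection". Under Visit 3, "On the day of surgery, the patient will take their last dose of everolimus", at least three hours before the operation.

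**When the decision is taken.** Section 1.5 says "After a minimum of three patients are treated for one week, if there is no evidence of serious adverse effects", treatment is extended by up to a week. Section 5.2 repeats this in nearly the same terms. Section 3.1 is looser: "after the safety of therapy is assured for this group, there will be an extension of the treatment to 14 days".

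**What follow-up exists.** The Medical Monitoring text under 6.5 has the investigators review safety data once each three-patient cohort has finished the trial, and sends data to the DSMB after every three patients. It also schedules weekly wound inspections until six weeks after surgery and treats any wound breakdown, dehiscence or infection as serious. Section 6.2.1 continues adverse event monitoring for at least 30 days after the last dose. Section 3.1 adds: "Subjects will be in the study for approximately 10 weeks".

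**The concern.** Infection and impaired wound healing around surgery are the risks the plan names in 1.5, and section 1.4 says the surgical risk of this regimen has never been documented. The stepwise 7-, 14- and 21-day design exists to look for those events before exposing anyone for longer. A trigger window that ends on the morning of surgery does not serve that purpose, and it contradicts Table 2. Separately, if extension follows as soon as the third patient has been treated, that patient's wound outcome is unknown, and the second patient's may be incomplete.

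One event among the first three should mean more patients at the same duration. If it surfaces after the decision, the next patient may already be on the longer course. The whole-study stop is a weaker safeguard, because it needs two wound healing problems or three serious infections among nine treated patients.

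**Working it through.** The plan states no operating characteristic for this rule, so there is no figure to reproduce.

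**Reading the text**

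- The window phrase sits only in the expansion sentence. The defect is therefore a conflict inside 5.2, between that sentence and Table 2. Section 5.2 also still contains a drafting reminder to come back to escalation and numbers.
- Trial completion is not dated. It could mean the off-study form due within two weeks of surgery (6.8.1), Visit 6 at 3 to 10 days after discharge, 30 days after the last dose, or the six-week inspection.
- The ten weeks: the Visit 1 note says "This visit will occur within 6 weeks of Visit 2" and goes on to say that this is when the patient is entered into the study. Section 4.4.2 agrees, putting entry 7 to 21 days before surgery. From entry, 10 − 1 = 9, 10 − 2 = 8 and 10 − 3 = 7 weeks remain after surgery in the three cohorts. All cover the six-week inspection.

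**Inputs**

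- 9 treated patients in 18 months (Study Summary): mean gap 18 × 30.44 / 9 = 60.9 days.
- Infection 5.3%, wound healing problems below 2% (sample size considerations): p = 5.3%, and 5.3 + 2 = 7.3%, taking the ceiling and adding.
- Assumed: p = 14.6% (double 7.3%) and 25%; exponential gaps between surgeries; onset uniform over 42 days after surgery; decision at the third surgery.

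**Incomplete follow-up at the decision.** With 42/60.9 = 0.69, the third patient is always incomplete. The second is incomplete with probability 1 − e^(−0.69) = 0.50, and the first with 1 − e^(−0.69)(1 + 0.69) = 0.15. The mean is 1 + 0.50 + 0.15 = 1.65 of 3.

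**Chance of extending, counts from the 5.2 text.** With full follow-up this is (1−p)³ + 3p(1−p)⁵. If only the last patient (third, or sixth after expansion) is unseen, it is (1−p)² + 2p(1−p)⁴.

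| | p = 5.3% | 7.3% | 14.6% | 25% |
|---|---|---|---|---|
| No event visible at decision, one appears later (simulation, 2,000,000 runs) | 6% | 9% | 15% | 21% |
| As above, and next patient starts before the event appears | 1.7% | 2.2% | 3.8% | 5.1% |
| P(extend), full follow-up | 97% | 95% | 82% | 60% |
| P(extend), last patient unseen | 98% | 97% | 88% | 72% |

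**Range for the first row**

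- Evenly spaced accrual: only the third patient is unseen at the decision, so p(1−p)² = 5 / 6 / 11 / 14%.
- One patient per three months: 6 / 8 / 14 / 18%.
- One patient per month: 8 / 11 / 19 / 27%.

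**The case against.** The strongest reply is that the plan already intends to look later. Table 2 names events that mostly arise after surgery. Section 3.1 requires safety to be assured. The Medical Monitoring review uses the same three-patient unit as the extension rule, and ten weeks from entry covers the wound inspection. On that view only a cross-reference is missing, and the phrase in the expansion sentence may merely identify the cohort.

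Much of this stands, and it rules out several stronger readings that a reader might infer:

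- *That the whole 5.2 rule ignores post-operative events.* The window is in one sentence only, and Table 2 says otherwise.
- *That the ten weeks may end before the wound check.* Counting from Visit 1 would leave as little as two or three weeks after surgery, but the documents put study entry at Visit 2.
- *That late events are lost.* They are recorded as serious, go to the DSMB if possibly related, and count toward the nine-patient stop.
- *That the exposure is 3–10%.* Multiplying the first row of the table by the 50% chance that someone starts within 42 days gives 3 / 4 / 7 / 10%. That also counts patients who start after the event is already visible. Requiring the start to come first roughly halves it.

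What the reply does not remove is the contradiction within 5.2 and the absence of any sentence that ties extension to the review.

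**Conclusion.** The point holds in limited form. The expansion trigger in 5.2, read literally, excludes the surgical-wound events that Table 2 counts, and the cohort review that would cure this is neither dated nor made a condition of extending.

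The effect is small. At the plan's own rates, a later event is unseen in about 6–9% of steps, about 2% of steps have a next patient already on the longer course before it appears, and the chance of extending moves by 1–2 points. It moves by 6–12 points only at the assumed rates of 14.6–25%. All of this supposes a decision at the third surgery, which the text permits but does not require. The accrual pattern and onset distribution are also assumed. With perfectly even 61-day spacing, the next patient would start after the six-week check.

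It is still worth correcting: safety is the primary analysis, this rule is what protects successive patients, and the change is a few sentences.

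**What to change.** In 5.2, with matching wording in 1.5 and 3.1:

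- Delete the phrase limiting the trigger to the treatment cohort period.
- State: *Events, including wound healing problems and infections, count from first dose through the six-week wound inspection. Treatment is lengthened only after the Medical Monitoring review of all patients required at the current duration. Patients who start before that review receive the current duration.*
- In the Medical Monitoring text, define trial completion as the six-week inspection and name the review as the extension decision. If the sponsor prefers 30 days after the last dose, say so, and note that later wound events are then not covered (12/42 = 29% of events if onset is even over six weeks).

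**Cost.** No new assessments are needed. However, the weekly inspections appear only in the Medical Monitoring text, the last numbered visit is 3 to 10 days after discharge, and most surgical patients live outside the city, so the six-week inspection should be added to the visit schedule.

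On average 42/60.9 = 0.69 patients per step stay on the shorter course, or 30/60.9 = 0.49 with the 30-day point. Table 2's no-event minimums use 3 + 3 + 1 = 7 of the 9 places, leaving two spare. The chance that more than two patients are displaced over two steps, leaving no 21-day patient, is P(Poisson(1.38) > 2) = 16%, or P(Poisson(0.99) > 2) = 8% with the 30-day point. Section 5.2 also says "At the 3 week dose duration, 6 patients will be treated even if there are no events among the first 3 patients". Those counts, 3 + 3 + 6 = 12, exceed 9 with or without this change.
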